COVER PAGE

Study Title: Addressing Health Disparities in Childhood Obesity, One Summer at a Time

Clinical Trials Registration Number: NCT03595332

Date of document: July 14, 2022

Statistical Analysis Plan

The proposed statistical analyses for the current study includes a nested regression model utilizing Generalized Estimating Equations with an exchangeable working correlation matrix to account for the nested data structure of children within schools and families. For all variables, 95% Confidence intervals will be reported (for b in models with a linear response variable and Odds Ratios for models with an ordinal logistic response variable) and a significance level of $p=0.05$ will be used to test hypotheses.

For the primary analysis, we propose to test the difference in Body Mass Index (BMI) Percentile-scores for age and sex based on Centers for Disease Control and Prevention (CDC) criteria from Baseline to 10-weeks using GEE models with a linear response variable. We will test whether the difference is significantly different from zero, adjusting for age (included as a covariate) and sex and ethnicity (included as factors). We will also test whether the immediate intervention group was significantly different from the delayed intervention group by including a variable denoting immediate vs delayed group membership. We will test the null hypothesis that participants in the intervention did not significantly change their BMI Percentile-score.

For the second primary analysis, we will test whether the BMI Percentile from baseline to 10-weeks was significantly different from zero among the highest-risk children, defined as those participants with a baseline BMI Percentile score equal to or greater than the 85th percentile as considered by the Centers for Disease Control and Prevention. GEE models will be used restricting the sample to children with overweight at baseline.

For the first secondary analysis, we propose to test the difference in Body Mass Index Percentile-score from Baseline to 1-year follow-up using GEE models with a linear response variable. We will test whether the difference is significantly different from zero, adjusting for age (included as a covariate) and sex and ethnicity (included as factors). We will test the null hypothesis that participants in the intervention did not significantly change their BMI Percentile-score.

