For the additional secondary analyses, we propose to test the difference in average self-efficacy score (1-5) from Baseline to 10-week follow-up using GEE models with an ordinal logistic response variable. We will test whether the difference is significantly different from zero, adjusting for age (included as a covariate) and sex and ethnicity (included as factors). We will test the null hypothesis that participants in the intervention did not significantly change their average self-efficacy score.

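### The self-efficacy response, ordinal model and null of zero do not fit together as written, and no immediate-versus-delayed comparison is named

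*SAP*

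**What the plan says.** The SAP's closing paragraph, on the additional secondary analyses, plans to test "the difference in average self-efficacy score (1-5) from Baseline to 10-week follow-up using GEE models with an ordinal logistic response variable". It continues: "We will test whether the difference is significantly different from zero, adjusting for age (included as a covariate) and sex and ethnicity (included as factors"). The null hypothesis is that "participants in the intervention did not significantly change their average self-efficacy score". No other model term is named.

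The SAP's opening paragraph adds two things. Results will be reported as "Odds Ratios for models with an ordinal logistic response variable", with 95% confidence intervals, and the GEE is meant "to account for the nested data structure of children within schools and families". Repeated visits within one child are not mentioned.

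The primary BMI percentile paragraph uses almost the same sentence about a difference from zero, but with a linear response. It also provides for a comparison of the two groups, "by including a variable denoting immediate vs delayed group membership". The self-efficacy paragraph has no such provision.

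The protocol's Measures section describes 13 questions across several behavioural constructs and gives one self-efficacy item as an example. It does not say how many items make up the self-efficacy score.

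**The concern.** The test sentence appears to have been carried over from the BMI analysis, where it works because a linear model for a change has an intercept that can equal the mean change. An ordinal logistic model has thresholds in place of that intercept, and its reported effects are odds ratios, whose no-effect value is 1.

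Two things are at stake. First, an analyst would have to choose the response, the model terms and the null value after the data are in, although this paragraph is the only pre-specification of the self-efficacy test. Second, a test of before-after change with no group term cannot separate the programme from the passage of time, the season or answering the same questions twice. A significant result could then be read as a programme effect without support.

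**Working it through.** The documents give no sample size, power or effect figure for self-efficacy, so there is no figure to reproduce. The check is of model structure.

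**Inputs from the SAP.** Outcome: average score on a 1-5 scale, baseline to 10 weeks. Model: GEE with ordinal logistic response. Terms: age, sex, ethnicity. Null: difference of zero. Output: odds ratios. Clustering: schools and families.

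**Benchmark: linear model for a change D.** E(D) = b0 + b1(age - mean age) + centred sex and ethnicity terms. Here b0 is the mean change at average covariate values, and b0 = 0 is the stated null. This is why the wording works for BMI percentile.

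**Reading A: the child's change is the ordinal response.** logit P(D <= j) = t_j - (b1 age + sex and ethnicity terms). The parameters are the thresholds t_j and the covariate effects. The odds ratios describe how change varies with age, sex and ethnicity. Whether there was any change is carried by the thresholds jointly. It could be tested only as a contrast among them at chosen covariate values, and the SAP specifies none.

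I fitted this model to simulated data (assumptions: one item scored 1-5, 2,000 children, age and sex with no true effect). The parameters were age, sex and 8 thresholds.

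| Simulated mean change | Age coefficient (p) | Sex coefficient (p) |
|---|---|---|
| -0.04 | 0.022 (0.20) | 0.081 (0.30) |
| 0.62 | 0.001 (0.94) | -0.013 (0.87) |

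Coefficients near zero are expected, since no covariate effect was simulated. The point is that a clear rise in the mean appears in none of the quantities that would be reported as odds ratios.

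**Reading B: the 1-5 score at each visit is the response.** logit P(Y <= j) = t_j - (g time + covariate terms). Now g = 0, an odds ratio of 1, is a direct test of no change. On simulated data, with visits clustered within child and an independence working structure:

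- No true shift: odds ratio 0.95, p = 0.33.
- True within-child log-odds shift of 1.0: odds ratio 2.31, p < 0.001.
- No true shift, 160 children, 400 runs: rejection rate 0.0575 at the 0.05 level. The Monte Carlo standard error is sqrt(0.05 x 0.95 / 400) = 0.011, so this is consistent with 0.05.

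Reading B is therefore workable, but set against the SAP text it lacks the following:

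| Needed | Stated in the SAP? |
|---|---|
| Score at each visit named as response | No |
| Time term | No |
| Visits clustered within child | No; schools and families only |
| How an average becomes ordered categories | No |
| Null of odds ratio = 1 | No; the null is a difference of zero |

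**Group term.** Under both readings the listed terms are age, sex and ethnicity. The primary BMI paragraph adds group membership; the self-efficacy paragraph does not.

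**The case against.** A reader might infer that the planned model has no parameter for the hypothesis and so cannot test it at all. The documents do not support that. The SAP never says that the change is the response. The stated 1-5 range fits the score itself, since a change would run from -4 to +4, and the promise of odds ratios fits Reading B, under which no change is a single parameter. Even under Reading A a threshold contrast could be built. This objection stands against any claim that the test is impossible. It does not remove the gap: the absent time term and the clustering named only for schools and families point towards Reading A, and neither reading can be run from the text.

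A reader might also infer that the average takes so many values that an ordinal model would need dozens of thresholds. That cannot be sized. The number of self-efficacy items is not given, and with one item, or an average rounded to whole numbers, an ordinal model is a conventional choice. Thresholds are also estimated only between observed levels.

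It is fair to say that the missing group term is separate from ordinal versus linear; the 1-year BMI analysis, which is linear, names none either. It is still a defect of this analysis. It is also fair that the stated null concerns change within participants, so a between-group model answers a different question. The fix therefore keeps the within-participant result as a descriptive one.

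**Conclusion.** The point holds as a mismatch and under-specification. Under the change-score reading, none of the odds ratios to be reported tests the stated null. Under the score-at-each-visit reading, the test is valid in principle, but the response, time term, categories, within-child clustering and null value are all unstated. Under both, no group comparison is named, so a change could not be attributed to the programme.

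No numerical size can be given from the documents. The simulations rest on assumed parameters and show only which parameters carry the test. Reading a group difference at 10 weeks as a programme effect further assumes that the delayed group had not started by then and that the groups were comparable at allocation; neither document describes this. The analysis is secondary, so the primary BMI conclusions are unaffected. It should be corrected, but it is not a critical fault.

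**What to change.** Replace the self-efficacy paragraph with a linear GEE: 10-week average self-efficacy score as response; immediate-versus-delayed group, baseline score, age, sex and ethnicity as predictors. Report the adjusted mean group difference with its 95% confidence interval. State how the average is formed and from which items.

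If the within-participant change is also wanted, report it as a descriptive result from a linear GEE on the change score, using the intercept with all covariates centred.

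If the ordinal model is kept, use the score at each visit as response with time, group and time-by-group terms, define the categories, account for visits within child, and state the null as an odds ratio of 1, with the time-by-group term as the group comparison.

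In each case, do not let robust standard errors rest on the four schools (protocol, Background) as the only clusters. Either cluster on family and include school as a factor, or use a small-sample correction. School as a factor works only if both groups occur within schools; if groups were assigned by whole school, it cannot be separated from group.

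The cost is SAP wording only; the group and baseline data are already in the plan. The downside is that a bounded score is treated as continuous, which is acceptable for a mean difference with sound standard errors.

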Demographic variables. Child's age (in years), sex (male or female), ethnicity (American Indian/Alaskan Native, Hispanic, White, Black/African American, Native Hawaiian/Pacific Islander or Two or more), grade level and school membership were collected by the school district. Height and weight were collected at each school during the school day by a community outreach coordinator trained in research quality measurements, supported by the school nurse and volunteers. Children were asked to take shoes and jackets off and items out of their pockets. Height to the nearest quarter inch was measured twice with a Charder HM200P Portstad Portable Stadiometer. Weight was measured to the nearest 0.1 pounds with a Health O Meter 752KL Heavy Duty Remote Display Digital Scale. Children's first weight status was considered their baseline, with $\leq 5^{\text{th}}$ BMI percentile for their age and sex considered underweight, 5^{th} to 85^{th} percentile healthy weight, $\geq 85^{\text{th}}$ percentile overweight and $\geq 95^{\text{th}}$ percentile as having obesity

Behavioral constructs. Health behavior constructs (13 questions) aligned with Social Cognitive Theory were assessed. Key constructs include self-efficacy ("I think I can be physically active even if it is hot or cold outside."), social norms (example: "My friends think that doing physical activity is fun"), and access or barriers to participation in physical activity and summer programs ("There are lots of places near where I live where I can do physical activities").

Reported activity and sedentary behaviors. A total of 8 questions ask about participation in the VERB program, types of activity in the past 7 days and participation in other summer programs. The number of activities reported were counted and compared before and after the intervention.

Recruitment:

Children were recruited directly at each school by research staff in collaboration with school physical education or health and wellness instructors. Recruitment occurred by providing flyers and tables at school events and drop-off/pick up. Parents were provided with a consent form and children with an assent form explaining the risks and benefits. English and Spanish versions were available. Upon completion of both forms, participants were measured and surveyed (see measurements below).

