Sample Size calculations: The estimated sample size needed to have sufficient power to detect a moderate effect size (using a Cohen's d of 0.3 as the reference) is 240 children, or 120 per arm. Based on our preliminary data, for each academic year, the average BMI change ranges from 0.35 to 0.55 units, with a standard deviation that varies across ethnic groups and years from 0.80

to 1.00. An example of an effect between two groups or time points that would match a Cohen's d of 0.3 would be one group in which the children on average increases their BMI by 0.5 units, and another group where participants increase their BMI by 0.2 units (0.3 unit difference), with standard deviations of 1.0. These effects (BMI difference of 0.3kgm^2) are just above the mean weighted effect size reported in the most comprehensive and recent meta-analysis on childhood obesity studies of 0.30kg/m^2 .^{9,10} With a two-tailed test and alpha level of 0.05, a sample size of 80 children per arm (a retention rate of 67%) would result in an associated statistical power $\geq 80\%$ to detect intervention effects between arms from one time point to the next. With very similar parameters and sample sizes, prior research has indicated that based on simulation studies,¹⁷ these parameters demonstrated excellent power ($\geq 80\%$) in detecting these size differences.

Institutional Review Board:

All protocol activities were approved by the Institutional Review Board of Northern Arizona University (protocol #1193689) and the Flagstaff Unified School District. Parental consent forms and children assent were attained for each participant.

References:

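### The 10-week self-efficacy analysis tests change against zero with no immediate-versus-delayed contrast, so a significant result cannot be attributed to the programme

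*SAP*

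**What the plan says.** The SAP paragraph on additional secondary analyses proposes to "test the difference in average self-efficacy score (1-5) from Baseline to 10-week follow-up using GEE models with an ordinal logistic response variable". The change is tested against zero, with age as a covariate and sex and ethnicity as factors. The paragraph closes: "We will test the null hypothesis that participants in the intervention did not significantly change their average self-efficacy score". No group variable is listed, and the SAP's opening paragraph on GEE adds none.

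The first primary analysis (BMI percentile, also baseline to 10 weeks) uses the same template but adds a second test, "by including a variable denoting immediate vs delayed group membership". The second primary analysis, restricted to children at or above the 85th percentile at baseline, states no group term.

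The protocol's Sample Size calculations section plans two arms: the number needed "is 240 children, or 120 per arm". It then gives power for effects between arms with 80 children retained in each. Neither document says when the delayed group receives the programme, who counts as a participant in the intervention for this analysis, or how children were allocated.

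**The concern.** Ten weeks is the one point at which the plan itself contrasts the immediate and delayed groups. A test of change against zero makes no use of that comparison for self-efficacy. Anything that moves the scores of all children between baseline and 10 weeks (season, answering the questionnaire a second time, growing older) is counted together with the programme.

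Rejecting this null shows only that scores moved. Read as a programme effect, it could be a false positive. A shift in the other direction could hide a real effect. The size of any such shift is unknown. The one self-efficacy item the protocol quotes, "I think I can be physically active even if it is hot or cold outside", mentions weather, and the scorecard in Appendix A runs from June to 6 August, so a seasonal component is conceivable. The documents do not show that one exists.

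**Working it through.** **The plan's own figure.** The only power statement is in Sample Size calculations and concerns BMI: at least 80% with 80 per arm, d = 0.3, two-sided 0.05. The retention figure reproduces (80/120 = 67%). The power does not: the non-centrality is 0.3 × √(80/2) = 1.90, which gives 47% in a two-sample t-test. The protocol also points to simulation studies in a cited source, which cannot be checked here. This shortfall is a separate matter; the figure is used below only as a benchmark.

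**Inputs.** From the protocol: 80 analysed per arm, two-sided 0.05. Assumed: d = 0.3 (the BMI value, since none is given for self-efficacy), a shift s common to all children in SDs of change, independent children, and a t-test on a continuous change score in place of the ordinal GEE.

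**What the zero-change test estimates.** Let d be the effect in exposed children and w the exposed share of those analysed.

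Estimate = w × d + s

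- Both groups pooled, delayed group unexposed, 80:80: w = 0.5, so the estimate is d/2 + s. With d = 0.3 and s = 0 it is 0.15.
- The same with an exposed share of 40% or 60%: 0.4 × 0.3 = 0.12, or 0.6 × 0.3 = 0.18.
- Immediate group only: w = 1, so the estimate is d + s.

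In both cases s remains. In the between-group contrast, (d + s) − s = d, provided s is the same in both groups.

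**Rejection rate with no programme effect (d = 0).** The non-centrality of the zero-change test is s × √n.

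| Shift s | 160 pooled | 80 immediate only | Between groups, 80 v 80, common shift |
|---|---|---|---|
| 0.1 | 1.26 → 24% | 0.89 → 14% | 5% |
| 0.2 | 2.53 → 71% | 1.79 → 42% | 5% |
| 0.3 | 3.79 → 97% | 2.68 → 76% | 5% |

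**The opposite error.** With d = 0.3 and s = −0.15, the pooled mean is 0.15 − 0.15 = 0 and the effect is missed 95% of the time. This value of s was chosen to cancel exactly; it shows the mechanism and does not predict a shift.

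**Power with d = 0.3 and s = 0.**

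- Pooled zero-change test: 0.15 × √160 = 1.90 → 47%.
- Between groups: 0.3 × √40 = 1.90 → 47%. The two agree because (d/2)√(2n) = d√(n/2).
- Immediate-only zero-change test: 0.3 × √80 = 2.68 → 76%.

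**Ordinal scale.** A proportional-odds model fitted to a 50:50 mixture, with assumed baseline categories of 5/10/25/35/25%, turns a true odds ratio of 2.0 into 1.40 and one of 4.0 into 1.91. For true odds ratios from 1.5 to 4.0 the pooled log odds ratio is 0.47 to 0.50 of the true one, so half is close but not exact.

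**The case against.** A reader might infer something stronger: that untreated delayed children are averaged in as if treated, so that the estimate is half the programme effect. The documents do not support that as a statement of fact. It needs the delayed group to be unexposed at 10 weeks, which the name implies but no passage says; the protocol's Activities section says that each participating child received a scorecard and gives no timing by group. It also needs both groups to be in the model. Pooling is the more natural reading, because the SAP states a restriction where it wants one (the overweight subset), and the first primary analysis, which must hold both groups, ends with a null in the same terms: "We will test the null hypothesis that participants in the intervention did not significantly change their BMI Percentile-score". But the wording could mean the immediate group alone. A further possibility is that each group's 10 weeks run from its own programme start, in which case no child is untreated and a between-group contrast would compare two treated groups.

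Other objections also stand in part:

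- The omission is not peculiar to self-efficacy, since the second primary BMI analysis lacks the term too.
- The 5% for the between-group test needs a shift common to both groups. Neither document describes random allocation or concurrent measurement.
- Neither document gives a survey schedule by group, so a 10-week self-efficacy reading in the delayed group is not confirmed.
- The quoted weather item asks about being active whatever the weather, and it is one example from a 13-question set. It is weak evidence of seasonal movement.
- Every s is assumed, d is borrowed from BMI, and clustering within schools and families is ignored.

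These points limit the size of the problem and how firmly it can be stated. They do not supply a between-group contrast.

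**Conclusion.** The concern holds in a conditional form. What is certain from the text is that the 10-week self-efficacy analysis tests change against zero, has no between-group contrast, and so leaves any common shift in the estimate whether the groups are pooled or only the immediate group is used. A significant result cannot be attributed to the programme. The dilution to about half is one scenario, dependent on pooling, an unexposed delayed group and roughly equal analysed numbers.

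The size depends on a shift the documents do not give. Over assumed shifts of 0.1 to 0.3 SD, false-positive rates run from about 24% to 97% (pooled) or 14% to 76% (immediate only), against a nominal 5%. The endpoint is secondary, so this should be corrected, but it does not threaten the primary analysis.

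**What to change.** In the SAP's additional secondary analyses paragraph:

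1. State which children are analysed, and whether the delayed group has received any of the programme by its 10-week reading.
2. Add the immediate-versus-delayed variable (or a group-by-time term) and make it the tested parameter for the programme effect. Keep age, sex and ethnicity, and account for baseline self-efficacy.
3. Restate the null as no difference between the immediate and delayed groups in self-efficacy change from baseline to 10 weeks.
4. Report change within each group descriptively.

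The cost is SAP wording and one model term that the SAP already defines, provided the delayed group was surveyed at 10 weeks. Against the pooled test there is no loss of power when group sizes are equal and there is no shift (47% for both at d = 0.3). Against an immediate-only zero-change test, nominal power falls from about 76% to 47% under the same assumptions. The higher figure is for detecting any change from baseline, so it is not power for a programme effect unless the shift is zero.
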